3.6. Eligibility criteria

Inclusion criteria:

Patient level inclusion criterion:

1. 18 years of age or older;

Eye level inclusion criteria - at least one eye must meet all of the following conditions

2. Non-infectious anterior, intermediate, posterior or panuveitis; either active or inactive uveitis is acceptable;
3. Macular edema (ME) defined as the presence of central subfield macular thickness greater than the normal range for the OCT machine being used ($>300\ \mu\text{m}$ for Zeiss Cirrus/Topcon 3DOCT or $>320\ \mu\text{m}$ for Heidelberg Spectralis), regardless of the presence of cysts, as assessed by study ophthalmologist;
4. Best corrected visual acuity (BCVA) 5/200 or better;
5. Baseline intraocular pressure $> 5\ \text{mm Hg}$ and $\leq 21\ \text{mm Hg}$ (current use of 3 or fewer intraocular pressure-lowering medications and/or prior glaucoma surgery are acceptable – *note that combination medications, i.e., Cosopt, count as 2 IOP lowering medications*);
6. Baseline fluorescein angiogram that is gradable for degree of leakage in the central subfield
7. Pupillary dilation sufficient to allow OCT testing.

Exclusion criteria:

Patient level exclusion criteria:

1. History of infectious endophthalmitis or infectious uveitis in either eye;
2. History of infectious scleritis of any type in either eye. (*Note: History of noninfectious scleritis that has been active in past 12 months is an eye-level exclusion –see #11 below.*)
3. History of keratitis (with the exception of keratitis due to dry eye) in either eye;
4. History of central serous retinopathy in either eye;
5. For women of childbearing potential: pregnancy, breastfeeding, or a positive pregnancy test; unwilling to practice an adequate birth control method (abstinence, combination barrier and spermicide, or hormonal) for duration of trial;
6. Use of oral acetazolamide or other systemic carbonic anhydrase inhibitor at baseline;
7. Oral prednisone dose $> 10\ \text{mg}$ per day (or of an alternative corticosteroid at a dose higher than that equipotent to prednisone $10\ \text{mg}$ per day) OR oral prednisone dose $\leq 10\ \text{mg}$ per day at baseline that has not been stable for at least 4 weeks (*note that if patient is off of oral prednisone at baseline (P01 visit), dose stability requirement for past 4 weeks does not apply*);

8. Systemic immunosuppressive drug therapy that has not been stable for at least 4 weeks;
9. Known allergy or hypersensitivity to any component of the study drugs;

Eye level exclusion criteria - at least one eye that meets all inclusion criteria cannot have any of the following conditions:

10. History of severe glaucoma as defined by optic nerve damage (cup/disc ratio of \geq 0.9 or any notching of optic nerve to the rim);
11. History of active noninfectious scleritis in past 12 months (*Note: History of noninfectious scleritis is acceptable if the last episode of active scleritis resolved at least 12 months prior to enrollment*);
12. Media opacity causing inability to assess fundus or perform OCT;
13. Presence of an epiretinal membrane noted clinically or by OCT that per the judgment of study ophthalmologist may be significant enough to limit improvement of ME (i.e., causing substantial wrinkling of the retinal surface)⁸¹;
14. Torn or ruptured posterior lens capsule
15. Presence of silicone oil;
16. Periocular or intravitreal corticosteroid injection in past 8 weeks;
17. Injection of dexamethasone intravitreal implant in past 12 weeks;
18. Placement of fluocinolone acetonide implant (Retisert) in past 3 years;

3.7. Randomization

After the patient has given written informed consent, eligibility has been confirmed and baseline data have been keyed and passed an electronic eligibility review, the patient will be randomly assigned to one of the three treatment groups, via a web-based system, returning the treatment assignment result in real time. Receipt of treatment assignment will be confirmed by user re-entry of the treatment assignment. Beginning at this point, the patient's data will be included for primary analyses, regardless of subsequent actual treatment and/or extent of adherence to therapy. Randomization will be accomplished using an auditable, documented scheme generating a reproducible order of assignment. Randomization schedules will be developed by the Coordinating Center (CC), using permuted blocks of varying lengths, designed to yield expected assignment ratio of 1:1:1. Randomization will be stratified by the presence or absence of concomitant systemic therapy for uveitis (e.g., oral corticosteroids and/or immunosuppressive drugs).

3.8. Data collection schedule

Visit ID	P01	P02	P03	P04	P05	P06
Time	Baseline	4-wk	8-wk	12-wk	20-wk	24-wk
Medical/ophthalmic history	X	X	X	X	X	X
Treatment history	X	X	X	X	X	X
Best-corrected visual acuity	X	X	X	X	X	X
Tonometry	X	X	X	X	X	X
Ophthalmic exam (slit lamp exam and ophthalmoscopy)	X	X	X	X	X	X
Gonioscopy	X					
OCT	X	X	X	X	X	X
Fundus reflex images	X					X
Fluorescein angiogram	X					
EuroQol Questionnaire	X	X	X	X	X	X
Visual Functioning Questionnaire - 25	X	X	X	X	X	X
Adverse event monitoring	X	X	X	X	X	X
Pregnancy testing [†]	X					

[†] Required for women of childbearing potential

4. Study treatment schedule and administration

4.1. Treatment overview

- The timing and administration of initial injections and earliest permissible second injections of assigned treatment are specified by the protocol. Treatment administration instructions and pre-injection IOP criteria are included in sections 4.2 and 4.3.
- Additional guidance is provided for treatment of non-responders and simultaneous enrollment of eligible patients in the MERIT Trial at certain time points.
- The protocol does not prescribe treatment options for every situation
- Treatment according to the best medical judgment of treating study ophthalmologist is permitted as deemed necessary. Repeat injections given before the protocol specified time points (section 3.3.) or other deviations from the treatment protocol should be reported expeditiously to CC on Unanticipated Event (UA) form, usually within a few days.

4.2. Treatment schedule

4.2.1. Initial injections of assigned treatment

- Patients will be randomized to receive an injection of one of three treatments; doses and routes of administration are those standardly used in clinical care:
 - Triamcinolone acetonide 40 mg given by the periocular route
 - Triamcinolone acetonide 4 mg given by intravitreal route
 - Intravitreal placement injection of the 0.7 mg dexamethasone implant
- Injection of assigned treatment should be given on the day of randomization or as soon after randomization as possible
- IOP requirements for injection of initial study treatment must be met on the day the treatment is administered:
 - ≤ 21 or mm Hg and treatment
 - ≤ 3 IOP-lowering agents (combination meds, e.g., Cosopt, count as 2 agents)

Note that the IOP requirements for the initial injection are the same as for eye eligibility for the trial. If study treatment is initiated on the same day as eligibility is confirmed and treatment assigned, no additional IOP measurements are needed. If circumstances require patient to return to clinic for injection at a later date, IOP must be checked and IOP-lowering agents evaluated prior to injection. If the eligibility requirements are not met, the injection should not be given. If the treating ophthalmologist elects to proceed with assigned treatment per best medical judgment, the deviation from the protocol must be reported to CC on an Unanticipated Event (UA) form; the UA form should be submitted as soon as possible usually within a few days.

4.2.2. Second injections of assigned treatment

Second injections of assigned treatment are permitted at or after specified time points if macular edema has not improved and re-treatment criteria are met. The time points and IOP limitations for second injections of periocular triamcinolone and intravitreal triamcinolone are consistent with typical clinical care approaches.

- Time points for second injection:
 - Periocular triamcinolone acetonide : 8 weeks *after* OCT (i.e., after ascertainment of primary outcome data)

- Intravitreal triamcinolone acetonide: 8 weeks *after OCT*
- Intravitreal dexamethasone: 12 weeks *after OCT*
- Reasons to give second injection:
 - Eye does not meet the improvement definition (a 20% decrease in central subfield thickness of the macula)
 - ME is worse after initial improvement
 - Eye has a normal central subfield thickness but has cystoid spaces in the 1 mm central subfield
- Re-treatment IOP requirements:
 - <25 mm Hg
 - ≤ 3 IOP-lowering agents (combination meds, e.g., Cosopt, count as 2 agents)

4.2.3. Treatment for non-responders (i.e., <20% reduction or worsening of ME)

Eyes that demonstrate less than a 20% reduction or worsening of ME as measured by the central subfield thickness on OCT at time points specified below will be considered primary treatment failures and will be handled in the following manner:

- Eyes in periocular triamcinolone arm at 12 weeks
 - Intravitreal triamcinolone acetonide 4mg if following conditions met:
 - IOP of <25 mm Hg and treatment with ≤3 IOP-lowering agents
 - Follow to close-out visit (week 24)
- Eyes in intravitreal triamcinolone acetonide arm at 12 weeks
 - Offer enrollment in the MERIT Trial if eligible OR treat according to best medical judgment
 - Follow to close-out visit (week 24)
- Eyes in the intravitreal dexamethasone arm at 20 weeks
 - Treat according to best medical judgment
 - Follow to the close-out visit (week 24)

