3.3. Trial schema

* Eye(s) meeting trial eligibility criteria receive initial injection of assigned treatment at P01 visit.

† Second injection of assigned treatment permitted at 8 week visit or later for periocular and intravitreal triamcinolone acetonide and at 12 week visit or later for intravitreal dexamethasone when following conditions are met:

- Eye does not meet the improvement definition (a 20% decrease in central subfield thickness of the macula) OR eye has a normal central subfield thickness but has cystoid spaces in the 1 mm central subfield OR ME is worse after initial improvement;
- IOP of <25 mm Hg and treatment with ≤3 IOP-lowering agents;

‡ Eyes demonstrating < 20% reduction or worsening of ME as measured by the central subfield macular thickness on OCT are considered primary treatment non-responders at these time points

§ Macular Edema Ranibizumab v. Intravitreal Anti-inflammatory Therapy (MERIT) Trial is a companion study to POINT (funded by the same grant) for treatment of macular edema persisting after intravitreal triamcinolone therapy. MERIT will begin enrollment approximately 1 year after the initiation of POINT and continue concurrently. POINT participants who meet MERIT eligibility criteria at indicated time points may enroll in MERIT while concurrently completing follow-up in POINT. MERIT will evaluate the relative effectiveness among two regionally-administered alternatives to regional corticosteroid injections, a) intravitreal ranibizumab (Lucentis®, Genentech Inc., San Francisco, CA), and b) intravitreal methotrexate (MTX), with c) the intravitreal dexamethasone (Ozurdex) for the treatment of uveitic macular edema persistent after intravitreal corticosteroids.

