3.5. Secondary outcomes

- Rate of IOP elevation of >21 mm Hg or \geq 10 mm Hg from baseline during the 24 weeks of follow-up
- Percent change in macular thickness as measured by OCT over the 24 weeks of follow-up
- Proportion of eyes with macular edema events over the 24 weeks of follow-up
 - \geq 20% reduction in macular thickness (or normalization of macular thickness even if there is <20% reduction)
 - "Resolution", defined as normalization of the macular thickness to within \pm 2 standard deviations of the normative mean for the OCT machine used
 - Worsening defined as a 20% increase in macular thickness from the lowest value after an injection
 - "Recurrence" defined as >20% increase in the central subfield measurement on OCT to an abnormal value in an eye that previously had resolution of ME
- Mean change in BCVA over the 24 weeks of follow-up.
Best-corrected visual acuity score will be measured at every study visit under standardized lighting conditions by certified study examiners masked to study treatment using logarithmic (ETDRS) visual acuity charts, according to the method described by Ferris, et al.⁷⁵
- Inflammation as graded using the semi quantitative scales used in the MUST Trial i.e., clinician grading of the presence and extent of anterior chamber cells, anterior vitreous cells, and vitreous haze based on previously published standard ordinal scales (0, trace, 1+, 2+, 3+, 4+)⁷⁶⁻⁷⁸ using the scales endorsed by the Standardization of Uveitis Nomenclature Working Group when applicable⁷⁹
- Safety outcomes including elevated IOP (>30 mm Hg thresholds); new onset posterior subcapsular (PSC) cataract or progression of pre-existing PSC (using the Age-Related Eye Disease Study [AREDS] scheme⁸⁰; vitreous hemorrhage; retinal tear/detachment; endophthalmitis; severe vision loss (\geq 15 Early Treatment Diabetic Retinopathy Study [ETDRS] letters) during the 24 weeks of follow-up.
- Cost-effectiveness of treatments for uveitic macular edema during the 24 weeks of follow-up will be assessed by enumerating costs of treatments and procedures for uveitis during the 24 week follow-up; participants' utilities will be measure with the EuroQol questionnaire.
- Visual function related quality of life as measured by the NEI Visual Function Questionnaire (25 item version).

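### The week-12 non-responder rule (4.2.3, footnote ‡ of 3.3) has no exception for an eye whose macular thickness is now normal, so a mildly thickened periocular eye can be resolved under 3.5 and still be listed for intravitreal triamcinolone

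*Combined protocol and SAP*

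**What the plan says.** Section 4.2.3 of the combined protocol and SAP concerns "Eyes that demonstrate less than a 20% reduction or worsening of ME as measured by the central subfield thickness on OCT". At the stated visits these eyes "will be considered primary treatment failures and will be handled in the following manner". The handling differs by arm:

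- Periocular arm, week 12: "Intravitreal triamcinolone acetonide 4mg if following conditions met". The conditions are IOP below 25 mm Hg and no more than three pressure-lowering agents.
- Intravitreal triamcinolone arm, week 12: an offer of MERIT if eligible, or best medical judgment.
- Dexamethasone arm, week 20: best medical judgment.

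Footnote ‡ of 3.3 uses the same threshold; such eyes "are considered primary treatment non-responders at these time points".

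Section 3.5 treats the same eyes differently. Its first macular edema event is a reduction of at least 20% "or normalization of macular thickness even if there is <20% reduction". A separate event, resolution, is "defined as normalization of the macular thickness to within" two standard deviations of the normative mean. Section 3.6 defines macular edema as "presence of central subfield macular thickness greater than the normal range for the OCT machine being used", with cutoffs of 300 µm (Cirrus/Topcon) and 320 µm (Spectralis), and requires no greater minimum thickening.

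Normal-thickness eyes do appear in the re-treatment criteria. Footnote † of 3.3 (and 4.2.2) lists as one reason for a second injection of the assigned drug: "OR eye has a normal central subfield thickness but has cystoid spaces in the 1 mm central subfield".

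**The concern.** Section 3.6 admits mildly thickened eyes, and such an eye can return to normal without losing 20% of its thickness. Section 3.5 provides for this; the treatment rule does not. The same eye at the same visit can therefore be resolved under 3.5 and a primary treatment failure under 4.2.3.

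In the two intravitreal arms only the label is wrong, because 4.2.3 leaves treatment open there. In the periocular arm the listed step is an intravitreal steroid for an eye that no longer has edema as 3.6 defines it. Section 4.4.2 puts IOP elevation after that drug at up to 40% of cases. That is a gross rate. These eyes have already had a periocular steroid, so the excess risk would be smaller.

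**Working it through.** **Where the two definitions part.** Let T be the upper limit of normal and b the baseline thickness. An eye at follow-up value x is normal if x ≤ T, and is labelled a failure if x > 0.8b. Both can hold only if 0.8b < T, so T < b < T/0.8. Section 3.5 gives no limits in µm, so I take T from 3.6 (assumption):

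- Cirrus/Topcon: 300/0.8 = 375 µm, so baselines above 300 and below 375 µm.
- Spectralis: 320/0.8 = 400 µm, so baselines above 320 and below 400 µm.

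Examples on Cirrus: 340 to 290 µm is 1 − 290/340 = 14.7% reduced and normal. An eye entering at 320 µm must reach 0.8 × 320 = 256 µm to escape the label.

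**Illustrative size.** The plan gives no figure to reproduce and no baseline thickness distribution. Inputs from 6.1: periocular mean reduction 25% (log 0.75) and SD of log change 0.33. I assume that week 12 resembles week 8, that second injections can be ignored, and that log change is normal.

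- P(less than 20% reduced) = 1 − Φ[(log 0.8 − log 0.75)/0.33] = 1 − Φ(0.196) = 0.422.
- P(normal and less than 20% reduced, given b) on Cirrus = Φ[(log(300/b) − log 0.75)/0.33] − Φ(0.196). This is 0.203 at 310 µm, 0.111 at 340 µm and 0.048 at 360 µm.
- Averaged evenly over 300-375 µm (assumption): 0.118. The Spectralis window gives the same value, because only b/T matters.
- Share of in-window labelled failures that are normal: 0.118/0.422 = 28%.

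If 20-50% of eyes enter in the window (assumption), the affected share of periocular eyes is 0.118 × 0.2 = 2.4% to 0.118 × 0.5 = 5.9%. The arm has about 89 × 1.25 × 0.9 = 100 followed eyes, so these are roughly counts as well.

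**Sensitivity.** Section 6.1 calls the SD of 0.33 conservative, so I also tried 0.20, with mean reductions of 20-30%.

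| Mean reduction | SD | Average in window | × 0.2 | × 0.5 |
|---|---|---|---|---|
| 30% | 0.33 | 0.106 | 2.1% | 5.3% |
| 30% | 0.20 | 0.126 | 2.5% | 6.3% |
| 25% | 0.33 | 0.118 | 2.4% | 5.9% |
| 25% | 0.20 | 0.167 | 3.3% | 8.3% |
| 20% | 0.33 | 0.125 | 2.5% | 6.3% |
| 20% | 0.20 | 0.195 | 3.9% | 9.8% |

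The range is about 2 to 10 per 100 periocular eyes. It is taken before the IOP condition and clinical judgment, and it includes eyes with central cysts, so unneeded injections would be fewer.

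**The case against.** **Section 4.2.3 may not bind.** Section 4.1 describes the non-responder text as guidance, says that the protocol does not prescribe for every situation, and permits best medical judgment. A sensible ophthalmologist would not inject an eye that has normalized. This largely stands, and many sites would withhold. It does not remove the label or the mismatch with 3.5, and the directive wording of 4.2.3 ("will be considered primary treatment failures and will be handled in the following manner") points the other way.

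A reader might infer that a site which withholds commits a reportable deviation. The documents do not settle that. Section 4.1 asks for deviations from the treatment protocol to be reported, but if 4.2.3 is guidance, withholding is not clearly a deviation.

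**The rule is about macular edema, and a normal eye has none.** This is arguable, but 4.2.3 measures edema by percentage change in thickness and never requires the thickness to be abnormal at that visit.

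**An outcome event and a treatment trigger need not share a definition.** True in general. Section 3.5 does not call normalization improvement, and the only stated improvement definition (3.3 and 4.2.2) is the 20% decrease. But a difference that lists an intravitreal steroid for eyes that 3.5 counts as resolved serves no evident purpose.

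**Section 4.2.2 has the same gap, so a reader might want it changed too.** It need not be. It only permits re-treatment, and only if edema has not improved. Adding normal thickness to its improvement definition would class normal-thickness eyes with central cysts as improved, against its own provision for treating them.

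**Conclusion.** The omission is real and minor. The text of 4.2.3 alone establishes it; footnote ‡ of 3.3 repeats it. The µm windows rest on taking the 3.6 cutoffs as the limits of normal. The figure of 2 to 10 per 100 periocular eyes also rests on an assumed share in the window, an even spread within it, and week 12 behaving like week 8. It is an illustration, since the documents do not allow the number to be computed.

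Two stronger conclusions are tempting and unsupported. A reader might infer that the efficacy result is compromised. It is not: the primary outcome is measured at week 8, before this rule applies, and no planned analysis counts primary failures. A reader might also infer that a defined comparison of additional injections is distorted. Section 2.1 names the need for further injections as a reason for 24-week follow-up, but 3.5 defines no such outcome and 6.2 no such analysis. What remains is possible unneeded exposure in a few periocular eyes, and a label that contradicts 3.5.

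**What to change.** In 4.2.3 and in footnote ‡ of 3.3, add to the non-responder definition: *except eyes whose central subfield thickness is normal (as defined in 3.5) at that visit and that show no cystoid spaces within the central 1 mm*.

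The cyst condition matters. The protocol regards normal-thickness eyes with central cysts as still treatable. If they were excepted as well, a periocular eye already re-injected at week 8 that was normal but cystic at week 12 would have no listed step. Those eyes stay under 4.2.3 as now, as do all eyes with abnormal thickness. Leave 4.2.2 and footnote † unchanged.

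The cost is one phrase in two places and a memo to sites. OCT is already scheduled at weeks 12 and 20, so no new data are needed, and no sample size or power figure changes.

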4.3. Treatment administration guidelines

Note: Ophthalmologist administering treatment may follow local of standard care guidelines for topical anesthesia and needle size if they have been reviewed by Study Clinic Director as appropriate for use in this trial.

4.3.1. Administration of periocular triamcinolone acetonide

The injection may be given either by posterior sub-Tenon's approach or by the orbital floor approach, as both appear to have similar efficacy; the approach to the periocular injection will be recorded for analysis if needed.

4.3.1.1. Posterior sub-Tenon injection

- Saturate a cotton-tipped applicator with topical anesthetic (e.g., in 1 or 2% lidocaine) and place under the upper lid for posterior sub-Tenon's approach
- Instruct patient to look inferonasally with eye to receive injection
- Retract upper lid

- Introduce needle (e.g., 16-mm 25 gauge needle) into the sub-Tenon space, bevel side down
- Advance needle with a lateral to and fro motion to ensure the tip does not engage sclera
- When needle is judged to be behind the macula, deliver 40-mg (1-mL) bolus of triamcinolone acetonide⁴³

4.3.1.2. Orbital floor injection

- Saturate a cotton-tipped applicator with topical anesthetic (e.g., 1 or 2% lidocaine) and place in inferior fornix where needle will be directed
- Introduce needle (e.g., 25-mm 25 gauge) at the lateral third of the inferior orbital rim
- Pass needle posteriorly parallel to the orbital floor periosteum to approximately 25 mm depth
- Slowly deliver 40-mg (1-mL volume) bolus of triamcinolone acetonide⁴³

4.3.2. Standard preparation for all intravitreal injections

Intravitreal injection procedures should be carried out under controlled aseptic conditions which include the use of sterile gloves and a sterile eyelid speculum (or equivalent). Adequate anesthesia and a broad-spectrum microbicide such as betadine, applied to the periocular skin, eyelid and ocular surface are required prior to an intravitreal injection.

